*: The visit window is extended to +/- 2 months (in addition to existing visit window) during the COVID-19 pandemic, to allow on-site visits (rather than remote visits) to occur as much as possible.

^a Observation visits every 30 days (± 7 days) until study drug is available.

^b Vital signs: blood pressure and heart rate will be measured prior to injection. On Day 360 (transition visit), vital signs will also be measured at 4 hours after injection.

^c ECG should be performed prior to the injection.

^d Hematology, chemistry (including glucose, liver and renal function, hsCRP, IL6, IFN- γ , and TNF- α), and coagulation testing (of which some will be collected and stored for future analyses). Blood samples for determination of laboratory values will be performed prior to study drug injection. All laboratory testing will be performed with subjects in a fasted state. See [Section 7.1.6](#) for a list of laboratory parameters. Lab tests performed by study's designated Central Lab facility from entry into the study to EOS. On days when inclisiran is injected, if indicated, the investigator will need to collect a blood sample for tryptase within 30 minutes of the onset of anaphylaxis (or as soon as logistically possible).

^e Physical and neurological examinations, weight, and ECG performed once yearly.

^f Visit windows are ± 2 days for the Day 30 visit, and ± 7 days from Day 90 onward.

^g Urinalysis collection is prior to the injection on Day 1; supplies from the Central Lab must be used to perform the urinalysis.

^h Urine pregnancy test performed and results available prior to the injection on Day 1; supplies from the Central Lab must be used to perform the test.

ⁱ Women of childbearing potential will have a pregnancy test at each visit.

^k Plasma glucose and lactate will be collected at intervals throughout the study and stored for future analyses. See [Section 7.1.8](#) for details. Additional blood samples will be collected every 180 days and aliquots of plasma and serum stored for future analyses.

^l Diary cards should be turned in to study site coordinator at follow-up visits on Day 30, 90, 180, 270 and 360.

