6.6.1 Inclisiran Transition Visit - Day 360 (Group 2; Switching Arm)

When subjects in Group 2 (switching arm) return to the study center at Day 360 (± 7 days), the first administration of inclisiran will be provided. Procedures will be as follows:

- [REDACTED]
- Vital signs: blood pressure and heart rate will be measured prior to injection
- Physical examination, including full neurological examination ([APPENDICX A](#)) and 12-lead ECG
- Central laboratory assessments (hematology, chemistry and coagulation testing)
- [REDACTED]
- Assessment of lipids/lipoproteins
- Urinalysis (local, using supplies provided)
- Pregnancy test (local, using supplies provided)
- Concomitant medications

- AE/SAE collection
- Study drug administration
 - First dose of inclisiran
 - For subjects in Transition 2, their first inclisiran administration should occur prior to the final administration of evolocumab (to be given up to 30 minutes after inclisiran administration using a separate injection site)

The following procedures will be performed 4 hours after the first inclisiran injection:

- Vital signs: blood pressure and heart rate

- Concomitant medications
- AE/SAE collection

6.6.2 Treatment & Follow Up Visits After Day 360

Refer to [Section 6.6](#) for the schedule of follow-up visits and the assessments to be completed following the Day 360 transition visit to inclisiran.

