### **Group 2 (Switching Arm):**

Subjects receiving evolocumab will receive the first dose on Day 1 (ORION-3), administered by the investigator at the site, and will then self-administer evolocumab at home every 14 days until Day 336. Sites will then be assigned to have their evolocumab treated subjects placed into one of two transition groups.

- Transition 1 (staged): Day 336 will be the final dose of evolocumab therapy and the first dose of inclisiran will be administered at the Day 360 visit.
- Transition 2 (concurrent): Day 336 will be the final dose of evolocumab therapy at home. At the Day 360 visit subjects will receive an additional dose of evolocumab and their first dose of inclisiran, both administered by the investigator.

After first study drug administration of inclisiran on Day 360, all subjects in Group 2 (switching arm) will be observed in the clinic for at least 4 hours post injection before being discharged.

The subsequent visit schedule is as follows:

- Dosing visits: Day 450 (2nd dose), then every 180 days until end of study (Days 630, 810, 990, 1170 and 1350).
- Safety follow-up visits: Days 390, 510, 540, 720, 900, 1080, 1260, and EOS (Day 1440).

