### Study day

Study day will be defined as the number of days since the date of first administration of study drug. The date of first administration of study drug will be defined as Day 1 and the day before the first administration of study drug will be defined as Day -1.

Therefore, for a particular date, study day will be calculated as follows:

For dates on or after the date of first administration of study drug,

$$\text{Study day} = \text{Assessment date} - \text{Date of first administration of study drug} + 1;$$

For dates prior to the date of first administration of study drug,

$$\text{Study day} = \text{Assessment date} - \text{Date of first administration of study drug}.$$

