## **2.7 Safety analyses**

All safety evaluations will be performed for the following groups unless otherwise specified:

- Subjects on evolocumab from the switching arm (Group 2) for the period between Day 1 (Day 1 of ORION-3) and Day 360.
- Subjects from the inclisiran only arm (Group 1), for the period from Day 1 (Day 1 of ORION-3) until EOS.

█ [REDACTED]

█ [REDACTED]

█ [REDACTED]

All the safety analyses will be performed on the safety population unless otherwise specified. Safety analyses are based on observed values. Any missing safety data including laboratory data will not be imputed.

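### SAP 2.7 ends the evolocumab safety period at Day 360 and does not tie it to each subject's actual first inclisiran injection

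*SAP*

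**What the plan says.** SAP 2.7 organises the safety evaluations by group and period. The evolocumab group is "Subjects on evolocumab from the switching arm (Group 2) for the period between Day 1 (Day 1 of ORION-3) and Day 360". SAP 2.7.1 carries the same groups into the adverse event tables. Further group bullets in 2.7 are redacted.

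The switch itself is a windowed visit. Protocol 6.6.1 states that when Group 2 subjects "return to the study center at Day 360 (± 7 days), the first administration of inclisiran will be provided". The Group 2 schedule (Protocol 6.1, Table 6-2) repeats the window: "Visit windows are ± 2 days for the Day 30 visit, and ± 7 days from Day 90 onward". In Transition 2 (Protocol 6.6.1), inclisiran is injected first and the last evolocumab dose follows within 30 minutes.

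Day 360 carries two meanings. SAP 2.1.1 makes a study day a calendar count: "Study day will be defined as the number of days since the date of first administration of study drug", and "The date of first administration of study drug will be defined as Day 1". For Group 2 that first drug is evolocumab. SAP 1.1 instead uses Day 360 as a visit name for Transition 1, where "the first dose of inclisiran will be administered at the Day 360 visit". The observation rule that follows opens with "After first study drug administration of inclisiran on Day 360, all subjects in Group 2", as if the injection always fell on that day.

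**The concern.** A subject's evolocumab-only exposure ends at the first inclisiran injection, and that injection can fall on any of 15 days. A period that ends at a fixed label does not follow it. No other readable rule repairs this. SAP 2.7.1 anchors treatment-emergent events to the first treatment in ORION-3, which is evolocumab in Group 2, so an event after the first inclisiran injection still qualifies for the evolocumab column if it falls inside the period.

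The outputs most exposed are those on acute reactions. Protocol 1.2.3 names injection site reaction as the only event known to be attributed to inclisiran, and SAP 2.7.1 plans four injection-site outputs as well as hypersensitivity. Protocol 1.3.1 says that the switching arm was added partly to compare safety and tolerability with evolocumab. An inclisiran reaction counted under evolocumab raises the comparator's rate. The same boundary also decides which laboratory and ECG data belong to the evolocumab year.

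**Working it through.** The plan gives no misclassification figure, so there is none to reproduce.

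**Inputs from the documents.** Switch visit: Day 360 ± 7, so Days 353 to 367, 15 possible days (Protocol 6.6.1 and Table 6-2). Period end: Day 360 (SAP 2.7).

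**Assumed, because the documents do not give them.** The distribution of actual visit dates within the window, and the lag from injection to onset.

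**Calendar reading: events moved into the evolocumab column.** With injection day *d* and onset lag *L*, an event is counted under evolocumab if *d* + *L* ≤ 360 (Day 360 included) or *d* + *L* < 360 (excluded). For uniform *d* the shares are (8 − *L*)/15 and (7 − *L*)/15, for *L* from 0 to 7.

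| Visit dates | Onset lag | Day 360 included | Day 360 excluded |
|---|---|---|---|
| Uniform, 353 to 367 | same day | 8/15 = 53.3% | 7/15 = 46.7% |
| Uniform | 1 day | 46.7% | 40.0% |
| Uniform | 3 days | 33.3% | 26.7% |
| Uniform | 7 days | 6.7% | 0% |
| Normal, centre 358, SD 3 | same day | 79.3% | 68.2% |
| Normal, centre 360, SD 3 | same day | 56.7% | 43.3% |
| Normal, centre 362, SD 3 | same day | 31.8% | 20.7% |
| Normal, centre 364, SD 3 | same day | 13.7% | 7.5% |
| All exactly on Day 360 | same day | 100% | 0% |

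The normal distributions are cut to the 353 to 367 window. With uniform visits and onset spread evenly over days 0 to 7, the shares are 30.0% and 23.3%.

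**Calendar reading: time lost from the evolocumab column.** With Day 360 included, a subject switched on Day 367 has Days 361 to 366 outside the period: 366 − 360 = 6 pre-inclisiran days.

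**Visit reading.** If Day 360 means the visit and the whole visit day is included, every same-day inclisiran reaction is counted under evolocumab. If the visit day is excluded, none is, but the assessments made before the injection are lost. Protocol 7.1.6 analyses hematology and full chemistry only on Days 1 and 360 in the first year, and 7.1.4 does the same for ECGs. Table 6-2 places the bloods and the ECG before the injection. Strictly applied, exclusion removes the only scheduled post-baseline hematology and ECG of the evolocumab year. No boundary set by whole days keeps these data and also excludes what follows the injection.

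**Weight of one event.** The documents give 382 enrolled (Protocol, Amendment 5) and 127 placebo among 497 treated in ORION-1 (Protocol 1.2.2). Assuming equal carry-over from both arms, Group 2 has about 382 × 127/497 = 98 subjects. One event is then 1/98, about 1 percentage point of the evolocumab column.

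**The case against.** The strongest reply is that Day 360 in SAP 2.7 names the transition visit. Protocol 6 splits the trial there, with a treatment period up to Day 360 and a follow-up treatment period from Day 360 in which all subjects are on inclisiran. SAP 2.7 may simply reuse that split. Its bullet also begins with subjects on evolocumab, which could limit it to time on that drug, and redacted bullets may hold a boundary or same-day rule.

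Much of this stands. The calendar reading is not the only one, and the wording is unclear rather than shown to be wrong. But Protocol 6 puts Day 360 at the end of one period and the start of the next, so it does not settle the boundary, and the visit reading has its own failure. The opening phrase sets no end point, and in Transition 2 both drugs are given at that visit.

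A reader might infer double counting, with the same event also appearing in a Group 2 inclisiran period. That period is not in the readable text, so the documents do not support the inference. A reader might also infer bias in one direction only. On the calendar reading, late switchers lose evolocumab time, and those in Transition 2 lose reactions to their last evolocumab dose, which lowers the evolocumab count.

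The setting also limits the consequence: the study is nonrandomised (Protocol 3.6.1), and the readable safety objective concerns Group 1 (Protocol 2.2).

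**Conclusion.** The point holds as a boundary that is not tied to the injection and not fully defined. On the SAP's calendar definition, switches on Days 353 to 360 put post-inclisiran time into the evolocumab column, and switches on Days 361 to 367 drop up to 6 pre-inclisiran days. The 47% to 53% figure applies to same-day reactions and needs the calendar reading together with visit dates uniform over the window. It is tempting to say outright that about half of all first-dose reactions will be misfiled. The documents give neither visit dates nor onset lags, later-onset reactions are affected less, and the share runs from 0% to 100% across visit-timing and boundary assumptions.

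In absolute terms few events are likely to move, each worth about 1 percentage point if Group 2 has about 98 subjects. The primary endpoint is untouched. The change should still be made, because each whole-day reading either misplaces events or drops assessments, and a better anchor is readily available.

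**What to change.** Define the evolocumab period as running from the first evolocumab injection up to, but not including, the subject's actual first inclisiran injection, or to last contact if the subject never switched. Then add three rules:

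- Assessments made before the injection at the switch visit stay in the evolocumab period.
- Adverse events starting on the injection day are assigned by recorded time or sequence where available, and otherwise to the post-inclisiran period.
- In Transition 2, events after the same-visit injections are reported as concurrent exposure. Only local reactions with a recorded injection site are attributed to one drug. This is needed because the last evolocumab dose follows inclisiran and would otherwise fall outside the evolocumab period with no rule of its own.

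The cost is a few sentences in SAP 2.7 and minor programming. The anchor is already in use: the exposure-adjusted rates in SAP 2.7.1 start at the inclisiran injection date, and SAP 2.4.1 calculates exposure from the date of the first inclisiran dose. Separate injection sites are required (Protocol 5.1.2), and injection-site reactions have their own eCRF pages (Protocol 8.2.4.2). The downside is small. The documents do not confirm that clock times are collected for injections or event onset, and some same-day events, systemic ones in Transition 2 above all, cannot be attributed to a single drug. If the redacted bullets already contain part of this, only the remainder needs adding.

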### 2.7.1 Adverse events (AEs)

Adverse events will be summarized for every group specified above in [Section 2.7](#).

The most recent version of MedDRA before DBL will be used for coding AEs. An AE (classified as preferred term) will be counted as a treatment emergent AE (TEAE) if the AE started after the first treatment in ORION-3 or the AE was present prior to the first treatment in ORION-3 but increased in severity after initiation of study drug in ORION-3. Only TEAEs will be summarized in the tables, but the subject data listings will include all AEs.

The following summary tables will be presented:

- Overall Summary of TEAEs
- TEAEs by primary system organ class (SOC) and preferred term (PT)
- TEAEs by PT
- TEAEs by primary SOC, PT, and severity
- TEAEs related to study drug by primary SOC, PT
- Treatment Emergent Serious AEs (TESAEs) by primary SOC and PT
- TESAEs by PT
- TESAEs related to study drug by primary SOC, PT
- TEAEs leading to withdrawal of study treatment by primary SOC and PT
- TEAEs with a fatal outcome by primary SOC and PT
- TEAEs at the injection site by primary SOC and PT
- Clinically relevant TEAEs at the injection site (listed in [Appendix 5.3](#)) by PT

- TEAEs at the injection site by primary SOC, PT and severity
- Prespecified signs and symptoms at the injection site

If more than one event occurred with the same preferred term for the same subject, the subject will be counted only once for that preferred term, using the most severe occurrence for the summary by severity. For select tables, exposure-adjusted incidence rate (EAIR) will be calculated for subjects from the inclisiran only arm (Group 1), for the period from Day 1 (Day 1 of ORION-3) until EOS, [REDACTED]

EAIR is defined as the total number of subjects with the event / total exposure (years) \* 100%, where total exposure = sum of duration from start date of inclisiran injection in ORION-3 to the onset date of the event (the last visit/contact date will be used for the patients without the event).

TEAEs at the injection site include all TEAEs identified as being an injection site reaction on AE Case Report Form (CRF) or with “injection site reactions” as the high level term (HLT).

The following additional adverse events will be assessed (Refer to [Appendix 5.2](#) for the detailed definitions):

1. Hepatic events
  2. Renal events
  3. Hypersensitivity
  4. Neurological events and Neurocognitive disorders
  5. Ophthalmological events
- [REDACTED]

Listings will be presented for subjects with death, SAEs, and AEs leading to a discontinuation.

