8.1.2 Serious Adverse Event

Any untoward medical occurrence that at any dose:

- Results in death
- Is life-threatening, ie, the subject was, in the opinion of the investigator, at risk of death at the time of the event. It does not refer to an event which hypothetically might have caused death of it were more severe
- Requires hospitalization or prolongs hospitalization
- Results in a significant, persistent or permanent change, impairment, damage or disruption in the subject's body function/structure, physical activities and/or quality of life,
- Is a congenital anomaly/birth defect, or
- Is another medically significant event where medical and scientific judgement should be exercised in deciding whether other situations should be considered serious reactions, such as important medical events that might not be immediately life threatening or result in death or hospitalization but might jeopardize the subject or might require intervention to prevent one of the other outcomes listed above. Examples of such events are intensive treatment in an emergency room or at home for allergic bronchospasm, blood dyscrasias or convulsions that do not result in hospitalization or development of dependency or abuse. Any suspected transmission via a medicinal product of an infectious agent is also considered a serious adverse reaction.

A distinction should be drawn between serious and severe AEs. Severity is an estimate or measure of the intensity of an AE, while the criteria for serious AEs are indications of

adverse subject outcomes for regulatory reporting purposes. A severe AE need not necessarily be considered serious and a serious AE need not be considered severe. For example, nausea that persists for several hours may be considered severe nausea, but not an SAE. On the other hand, an MI that may be considered minor could also be an SAE if it prolonged hospitalization.

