8.2.2 AE Severity

The severity of every AE must be assessed by the investigator using a three-point grading system.

1 = Mild: Discomfort noticed, but no disruption to daily activity. Requires minimal or no treatment.

2 = Moderate: Discomfort sufficient to reduce or affect normal daily activity. Requires therapeutic measures.

3 = Severe: Inability to work or perform normal daily activity. May require systemic drug therapy or other treatment.

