8.4.2 Sponsor Discontinuation Stopping Criteria

The Sponsor will review data on an ongoing basis and may, on discussion with the DMC, terminate the study for any clinically significant drug related safety signal (eg, serious hypersensitivity reactions or drug induced liver injury, etc.).

Premature termination of a study may also occur because of a regulatory authority decision, change in opinion of the IRB/EC, drug safety problems, or at the discretion of Sponsor . In addition, Sponsor retains the right to discontinue development of inclisiran at any time.

If a study is prematurely terminated or discontinued, Sponsor will promptly notify the investigator. After notification, the investigator must contact all participating subjects and the hospital pharmacy (if applicable) within 30 days of the notification. Final study visits should occur within 30 days of subject contact. As directed by Sponsor , all study materials must be collected and all care report forms (CRFs) completed to the greatest extent possible.

The Sponsor will inform the health authorities and the IRBs/EC that the study has been stopped and the reasons for doing so, within the locally applicable timelines.

9 Data Collection

An electronic data capture (EDC) system will be used for this study. All users will be trained on the technical features of the EDC as well as the content of the eCRF by qualified personnel prior to gaining access to the EDC. A UserID/Password will be granted after training. This ID is not to be shared amongst the study staff. All users must have a unique account to enter or review data. The eCRF should be filled out by the site 3 days after each visit. It is not expected that the eCRF will serve as source for any data collected in this study. If there is a reason for a site to do so, it must be approved by MDCO and documented in the site files.

This study will utilize the same EDC system used in the ORION-1 study to collect the data defined by this protocol, [REDACTED]. Data already collected for medical history, ongoing concomitant medications, and ongoing adverse events will be retained and utilized in analysis as defined by the SAP.

Prior to the database being locked, the investigator or designee will review, approve, and sign/date each completed eCRF. This signature serves as attestation of the investigator's responsibility for

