10.3.4.1 Adverse Events

The Medical Dictionary for Regulatory Activities (MedDRA) dictionary will be used for coding AEs. An AE (classified as preferred term) occurring during the treatment periods will be counted as a treatment emergent AE (TEAE) either if it is not present at Day 1 (Day 1 of ORION-3) or if it is present at Day 1 (Day 1 of ORION-3) but increased in severity during the treatment periods. Any AEs/SAEs that occur prior to dosing under this extension study will be assessed as part of the evaluation of the ORION-1 safety database.

The number (percentage) of subjects reporting TEAEs for each preferred term will be tabulated by system-organ class, by system-organ class and severity, and by system-organ class and relationship to study drug. If more than one event occurred with the same preferred term for the same subject, the subject will be counted only once for that preferred term using the most severe or related occurrence for the summary by severity, or relationship to study drug, respectively.

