### **2.7.2 Deaths**

As mentioned in [Section 2.7.1](#), TEAEs with a fatal outcome will be summarized by SOC and PT.

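### An adverse event ongoing at ORION-3 Day 1 that turns serious or fatal without a rise in severity grade is left out of the serious-event and death tables

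*SAP*

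**What the plan says.** SAP 2.7.1 gives an AE two routes to being a TEAE. Either it starts after the first ORION-3 treatment, or "the AE was present prior to the first treatment in ORION-3 but increased in severity after initiation of study drug in ORION-3". Protocol 10.3.4.1 has the same second route: an event "present at Day 1 (Day 1 of ORION-3) but increased in severity during the treatment periods". Neither document adds a route through seriousness or outcome.

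The definition controls the output: "Only TEAEs will be summarized in the tables, but the subject data listings will include all AEs". The serious-event tables in SAP 2.7.1 are tables of treatment-emergent serious AEs (TESAEs). On deaths, SAP 2.7.2 says only that "TEAEs with a fatal outcome will be summarized by SOC and PT".

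Protocol 8.2.2 grades severity as mild, moderate or severe. The top grade is defined by function and treatment need: "3 = Severe: Inability to work or perform normal daily activity". Protocol 8.1.2 separates this from seriousness: "A severe AE need not necessarily be considered serious and a serious AE need not be considered severe".

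Protocol section 9 carries earlier events forward: "ongoing adverse events will be retained and utilized in analysis as defined by the SAP". SAP Table 2-1 closes medical history at Day 1 of ORION-1 and treats later new conditions as AEs.

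**The concern.** Long-term safety and tolerability of inclisiran in Group 1 is a stated secondary objective (Protocol 2.2), and serious events and deaths are central to it. A rule that looks only at start time and severity grade cannot register a change that happens in seriousness or outcome alone.

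The plan's own design creates a pool of events open at Day 1. A condition that first appeared during ORION-1 (at least 210 days), in the gap period or in the observation period is an AE, not medical history, and may still be ongoing when ORION-3 dosing starts. Group 1 subjects received inclisiran in ORION-1, so some of these events may have begun after exposure to the drug. Protocol 10.3.4.1 assigns events before dosing to the ORION-1 safety evaluation. It does not say what happens when such an event turns serious or fatal during ORION-3 dosing, and Protocol 1.2.2 describes ORION-1 as complete.

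**Working it through.** There is no planned figure to reproduce. The check applies the TEAE rule to the severity scale.

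**Inputs**
- Severity grades 1, 2 and 3 (Protocol 8.2.2), with no life-threatening or fatal grade.
- TEAE rule for an event present before the first dose: the grade must rise (SAP 2.7.1; Protocol 10.3.4.1).
- Serious-event and death tables limited to TEAEs (SAP 2.7.1 and 2.7.2).

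**Step 1: grade pairs.** Let g be the grade at Day 1 and h the worst later grade. The event is a TEAE only if h > g. There are 3 × 3 = 9 pairs:

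| | h = 1 | h = 2 | h = 3 |
|---|---|---|---|
| g = 1 | no | TEAE | TEAE |
| g = 2 | no | no | TEAE |
| g = 3 | no | no | no |

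Three pairs qualify (1 to 2, 1 to 3, 2 to 3). The three same-grade pairs do not qualify, whatever the later seriousness or outcome. For g = 3 no pair qualifies, because there is no higher grade.

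**Step 2: consequence for the tables.** A same-grade event that becomes serious is not a TEAE, so it is not a TESAE. A same-grade event that proves fatal is not a TEAE, so it is not in the SAP 2.7.2 summary.

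**Step 3: where it still appears.** SAP 2.7.1 lists all AEs and also lists subjects with deaths and serious AEs. SAP 2.3.1 tabulates reasons for early discontinuation by group, and Protocol 4.4 names death as one. That gives a count of deaths that end participation, but not by cause.

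**Step 4: direction and size.** TESAEs are a subset of all serious AEs after first dose, and fatal TEAEs are a subset of events leading to death after first dose. The tabulated count can therefore equal or fall below the on-study count, but never exceed it. Size would need the number of events ongoing at Day 1 and the share that turn serious or fatal at the same grade. The documents give neither.

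**Step 5: exceptions.** SAP 5.1.2 treats events with incomplete dates as treatment-emergent unless the dates show an earlier start, which helps only those events. Parts of SAP 2.7 and 2.7.1 are blacked out. The TEAE definition, the readable table list and section 2.7.2 contain no exception.

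**The case against.** The case on the other side is substantial, and much of it stands.

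- **Eligibility.** The tempting example is a cancer found in ORION-1 or the gap that later kills the subject. The gap ends at ORION-3 consent. Exclusion 1 removes uncontrolled or serious disease that may interfere with participation or put the subject at significant risk, and exclusion 3 removes illness with a life expectancy shorter than the trial, naming cancer. Most such cases should not enter. What remains is a misjudged prognosis, a condition arising between entry and Day 1, or a milder event that becomes serious.
- **Grade often rises.** An event that newly leads to hospital or death will often meet the definition of Severe. If it was mild or moderate before, it then becomes a TEAE.
- **Coding.** TEAEs are classified by preferred term. Progression recorded under a new term with onset after the first dose counts outright. The documents give no rule requiring this, so it narrows the gap but does not close it.
- **Nothing is concealed.** A reader might infer that these events vanish from the report. They do not: the listings and the disposition table show them as described above. What is missing is a count by SOC and PT, or by cause.
- **Death totals that differ.** A reader might infer an error if the fatal-TEAE table and the disposition table disagree. They use different populations (safety and ITT) and answer different questions, so a difference alone is not an error.
- **The rule is the protocol's own.** A reader might infer that the SAP departs from the protocol. It does not. Rewriting the TEAE definition in the SAP alone would create a departure, while SAP section 4 states that no protocol-specified analysis was changed.

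**Conclusion.** The point holds in a limited form. An event ongoing at Day 1 that becomes serious or fatal on study drug is absent from the TESAE and fatal-TEAE tables when it stays under one preferred term and its grade does not rise. That follows directly from the text and needs no numerical assumption.

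The size is unknown and probably small. A reader might want to name a number of missed subjects or a percentage of missed deaths. The documents support neither, because they give no count of ongoing events and no event rates. The judgement that the number is small rests on exclusions 1 and 3 being applied as written and on many worsening events rising in grade or taking a new term. The direction is certain: the restriction can only reduce the tabulated counts. This calls for a cheap improvement to the reporting; it is not a flaw that undermines the safety analysis.

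**What to change.** Keep the protocol's TEAE definition and every planned TEAE table. Then make three additions:

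1. **SAP 2.7.2:** *All deaths from the first ORION-3 dose to end of study will be tabulated by group and primary cause, regardless of when the causal AE began.*
2. **SAP 2.7.1:** *All SAEs reported from the first ORION-3 dose to EOS will be tabulated by SOC and PT, regardless of TEAE status.*
3. **SAP section 4:** record both tables as additions to the protocol-specified analyses, in place of the statement that nothing changed.

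Protocol 8.3.1 already requires every SAE from Day 1 through EOS to be reported to the sponsor, so the SAE table needs no new collection. Selecting on reported SAEs also avoids relying on a dated change of seriousness within an existing AE record, a field the documents do not describe.

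The cost is two extra tables, and serious-event and death counts that may be slightly less favourable.
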